#### SCHEMA

Protocol 2011-0465 ASeptember 6, 2017 Page 3 of 50

#### **1.0 OBJECTIVES**

- 1.1. Primary objectives
  - Evaluate safety and efficacy of treatment with pazopanib for 6 months in patients with VHL who have a measurable VHL related lesion.
- Secondary objectives
  - Evaluate rate of growth over time in target lesions before and after pazopanib treatment
  - Evaluate need for surgical intervention over time in patients who receive pazopanib and compare to rate prior to receipt of drug
  - Create an annotated tissue resource from patients with VHL for use in future research related to cancer.
  - 1.2. Preclinical objectives
    - Evaluate circulating factors in patients with VHL undergoing treatment with pazopanib
    - Evaluate relationship between VHL genotype and response to pazopanib.

#### 2.0 BACKGROUND

2.1 Von Hippel Lindau Syndrome

The VHL syndrome affects approximately 1 in 35000 live births each year worldwide. The disease results from an autosomal-dominant mutation associated with deletion of the *VHL* gene located on the short arm of chromosome 3. The VHL protein is directly responsible for downregulating hypoxia-inducible factor alpha (HIF) transcription factors responsible for several angiogenic responses to hypoxia. Thus, mutations of the VHL gene lead to the regulatory loss of HIF, with increased intracellular HIF during normoxia being the primary common pathway leading to the downstream manifestations of the syndrome via induction of VEGF, PDGF, erythropoietin, and a variety of other angiogenic pathways. The clinical presentation of this syndrome is characterized in late childhood and early adulthood by hemangioblastomas of the brain, spine, and retina, in addition to renal cell carcinoma, pheochromocytoma, neuroendocrine tumors of the pancreas, other benign tumors (e.g., endolymphatic sac tumors) as well as cystic lesions in various organs such as the kidneys and pancreas. Renal cell carcinomas and hemangioblastomas are directly related to HIF pathway activation, while pheochromocytomas appear to be induced via non-HIF pathways. The multi-organ morbidity of these lesions as well as their treatment is significant in these patients, who must often endure repeated, serial interventions of the CNS, eye, kidneys, pancreas, adrenal, and other organs. While little data has been published in regard to the multiplicity of interventions for all the involved organ systems, one report has shown that by age 30, most patients with VHL have had greater than 2 interventions for any involved organ. Of those with RCC, 88% required intervention at an average range of 1.4 to 3 interventions per year. Renal and CNS tumors comprise the majority of those causing

Protocol 2011-0465 ASeptember 6, 2017 Page 6 of 50

the greatest impact, as does their treatment.

Genetic characterization of the various mutations has been classified as Type 1 (no pheochromocytoma) and Type 2 (presence of pheochromocytoma) which is further characterized into 2a, low risk of renal cancer, 2b, high risk of renal cancer; and 2c, pheochromocytoma only.

#### 2.2 Pazopanib

Angiogenesis, the process of new blood vessel formation, plays an important role in the development of malignancy as well as the growth and progression of metastatic lesions. The molecular pathways involved in angiogenesis have been targeted for anti-tumor therapy. Numerous growth factors and cytokines are involved in the angiogenic process. Among these factors, vascular endothelial growth factor (VEGF) has a predominant role as a central mediator of tumor-related angiogenesis, and its expression has been shown to be an adverse prognostic factor for a number of solid tumors.

Pazopanib is an orally-bioavailable, ATP-competitive tyrosine kinase inhibitor of VEGFR (-1, -2, and -3), PDGFR (- $\alpha$  and - $\beta$ ) [AjtandRazopanib is being developed by Novartis Pharmaceuticals for the treatment of a variety of cancers. In nonclinical experiments, pazopanib has demonstrated encouraging potency and selectivity for VEGF receptors: for example, pazopanib demonstrated significant inhibition of VEGF-induced VEGFR-2 phosphorylation in human umbilical vein endothelial cells and was 3- to 400fold selective for VEGF receptors compared to 23 other kinases tested. Pazopanib showed significant growth inhibition of a variety of human tumor xenografts in mice, and also inhibited angiogenesis in several different models of angiogenesis (e.g., the Matrigel plug assay, the cornea micropocket, and the laser-induced choroidal neovascularization models).

Pazopanib 800 mg once daily is the recommended monotherapy dose based on clinical and preclinical results. Once daily doses of 50 mg to 2000 mg pazopanib were investigated in the "First Time in Human", Phase I Study VEG10003. Increases in the pazopanib dose above 800 mg once daily when administered in the fasted state did not result in a consistent increase in systemic exposure at steady-state. Therefore, no further benefit is expected at pazopanib doses above 800 mg once daily.

Pharmacodynamic data indicate that pazopanib, at a monotherapy dose of 800 mg once daily, results in effects consistent with inhibition of the VEGF receptors it was designed to target. Concentration-effect relationships were observed between trough plasma pazopanib concentrations and the development of hypertension in Study VEG10003 and the percent change from baseline in sVEGFR2 nadir in Study VEG102616. The trough plasma pazopanib concentrations associated with one-half the maximal effect (EC50) in both concentration-effect relationships were similar (21.3  $\mu$ g/mL and 15.3  $\mu$ g/mL) and demonstrate that there is a consistent inhibition of VEGF receptor(s) in subjects with

Protocol 2011-0465 ASeptember 6, 2017 Page 7 of 50

cancer when plasma pazopanib concentrations are maintained above 15  $\mu$ g/mL. The plasma pazopanib EC50 values for biologic effects observed in the clinical studies are similar to the plasma concentration of 40  $\mu$ M (17.5  $\mu$ g/mL) required for optimal inhibition of VEGFR-2 phosphorylation in mice [GSK Report RH2003/00005/00]. Progression Free Survival (PFS) in subjects with renal cell cancer in study VEG102616 was compared between subjects whose trough plasma pazopanib concentrations at Week 4 were above or below selected threshold values that were distributed evenly across the observed predose concentrations. Subjects with trough concentrations above the threshold values had significantly better PFS, compared to the remaining subjects, when the threshold concentrations were 12.6  $\mu$ g/mL, 17.4  $\mu$ g/mL, and 20.7  $\mu$ g/mL. Use of thresholds higher than 21  $\mu$ g/mL did not result in a significant difference in PFS between patients above and below the threshold. Using thresholds of 15  $\mu$ g/mL and 20.7  $\mu$ g/mL, patients with trough concentrations above the threshold salso had significantly better response rate and tumor shrinkage than the remaining patients.

Pazopanib C24 at steady-state was greater than 15  $\mu$ g/mL in 93% of subjects who received 800 mg once daily in Study VEG10003. Individual subjects receiving pazopanib doses below 800 mg once daily can achieve plasma concentrations over 15  $\mu$ g/mL, albeit at a lower frequency compared with what is observed at 800 mg once daily. Therefore, the pharmacokinetic and pharmacodynamic results across clinical studies demonstrate that pazopanib 800 mg once daily results in plasma concentrations that provide optimal biologic effects associated with VEGFR inhibition in the greatest proportion of subjects.

Additional support for an 800 mg once daily pazopanib dose comes in results from Study VEG105192, a 435-subject Phase III study of pazopanib (800 mg once daily) versus placebo in treatment-naïve and cytokine-pretreated subjects with renal cell carcinoma (RCC). In this study, the median progression-free survival (PFS) in the pazopanib arm was 9.2 months (95% CI, 7.4, 12.9) compared to 4.2 months (95% CI, 2.8, 4.2) in the placebo arm. This finding represented a statistically significant improvement in PFS in response to pazopanib monotherapy (HR 0.46, 95% CI 0.34 to 0.62, p<0.0000001). In addition, the response rate (defined as the percentage of subjects achieving either a confirmed complete or partial response according to RECIST) in the pazopanib arm was 30% versus 3% in the placebo arm, and the median duration of response in pazopanib-treated subjects was 58.7 weeks. Results from Study VEG105192 therefore clearly indicate that an 800 mg once daily dose of pazopanib is highly effective in treating subjects with advanced RCC.

Clinical data from more than 20 clinical Phase I, II, and III studies are available. As of the cutoff date, 09 September 2008, approximately 1600 subjects with cancer have received pazopanib in clinical studies conducted by Novartis Pharmaceuticals or NCI. Clinical data indicate that (a) pazopanib is absorbed after oral administration, (b) the 800 mg daily dosing regimen is an active monotherapy dose for subjects with cancer, providing optimal biologic and clinical effects associated with VEGFR inhibition, (c)

Protocol 2011-0465 ASeptember 6, 2017 Page 8 of 50

pazopanib is generally well-tolerated at the 800 mg daily dosing regimen, and (d) pazopanib has encouraging efficacy in specific tumor settings such as RCC, sarcoma, NSCLC, cervical and ovarian cancer.

The most common adverse events reported for pazopanib monotherapy to date are diarrhea, fatigue, nausea, hypertension, hair color changes (hair depigmentation), anorexia, vomiting, dysgeusia, headache, abdominal pain, rash, aspartate aminotransferase (AST) and alanine aminotransferase (ALT) increases, constipation, cough, and arthralgia. Most of these events were Grade 1 or 2 using the National Cancer Institute-Common Toxicity Criteria of Adverse Events, Version 4.0 (NCI-CTCAE, v4.0). The most frequent Grade 3 or 4 events were hypertension, fatigue, diarrhea, and AST and ALT increases. Less common AEs of note include hand-foot syndrome, mucositis/stomatitis, proteinuria, venous thrombotic events, and bleeding. Intestinal perforations and arterial thromboses were uncommon. The most common serious adverse events (SAEs), derived from all pazopanib studies that include studies where pazopanib was administered in combination with chemotherapy, are diarrhea, abdominal pain, vomiting, dyspnoea, hypertension (including one report of hypertensive crisis), pyrexia, anaemia, dehydration, fatigue, pneumonia, pleural effusion, neutropenia, pulmonary embolism, increase in ALT and nausea. Two cases of Torsades de Pointes have been reported in the pazopanib clinical program; however, whether or not there is a causal relationship to pazopanib remains unclear. A number of these events are known class effects of VEGF inhibitors. Therefore, this protocol is designed to closely monitor and provide clear management guidelines for these events based on the clinical experience with pazopanib to date.

2.3 Clinical and Preclinical Studies Assessing Response to Sunitinib in VHL, and Assessment of Endothelial Receptors in Renal Tumor and Hemangioblastoma Endothelium

A concerted effort to elucidate the functional consequences of a mutated VHL gene revealed that VHL is a key regulator of cellular hypoxia signaling. VHL controls protein levels of hypoxia-inducible factor 1 alpha (HIF1 $\alpha$ ) and HIF2 $\alpha$ , transcription factors that heterodimerize with HIF1 $\alpha$  and result in the transcription of proangiogenic proteins in an HIF $\alpha$  isoform–dependent manner.Agents developed to alter the downstream consequences of VHL inactivation and inappropriate angiogenesis include bevacizumab, an anti-VEGF antibody, and sorafenib, sunitinib, and pazopanib, which are smallmolecule inhibitors of VEGF receptors (VEGFRs). Because all four of these agents demonstrated significant efficacy in patients with metastatic sporadic clear-cell RCC, which harbors the VHL mutation in most cases, they were approved by the U.S. Food and Drug Administration for the treatment of advanced RCC.

The effect of these agents on VHL-specific lesions is not well known. We hypothesized that if the major functional consequence of VHL mutation is inappropriate angiogenesis,

Protocol 2011-0465 ASeptember 6, 2017 Page 9 of 50

then blocking VEGF signaling with a potent and specific VEGFR inhibitor will alter the growth pattern of all VHL-related lesions. To test this hypothesis, we initiated a clinical trial in which we treated individuals who have genetically proven VHL with sunitinib. Because interim findings on efficacy suggested that RCCs and HB respond differently to sunitinib, we analyzed the expression and activation of various molecular markers (endothelial VEGFR, PDGFR, Tie-2, fibroblast growth factor receptor 3 [FGFR3], and fibroblast growth factor receptor substrate 2 (FRS2), an intracellular signaling molecule specifically activated by FGFRs) in 20 archived tissue specimens each from sporadic RCCs and VHL-related HBs.

## 2.3.1 Clinical Outcome Data with Sunitinib

At least one follow-up imaging study was conducted on all patients. Table 1 shows the best responses of individual lesions according to RECIST.

	Best Response					
		N (%)				
	No. of	Partial	Stable	Progressive		
Lesion Type	Lesions	Response	Disease	Disease		
Hemangioblastoma	21	0	19 (91)	2 (9)		
Renal cell carcinoma	18	6 (33)	10 (67)	2 (10)		
Renal cyst	9	0	9 (100)	0		
Retinal angioma	7	0	7 (100)	0		
Pancreatic NET	5	0	5 (100)	0		
Pancreatic cyst	3	0	3 (100)	0		

## Table 1. Best Response of von Hippel-Lindau Lesions by RECIST after Sunitinib

Abbreviations: RECIST, Response Evaluation Criteria in Solid Tumors; NET, neuroendocrine tumors.

Of the 21 evaluable individual HB lesions, there were no partial responses (PR). In comparison, 6 of 18 RCC lesions responded with a PR, (P=0.014). All five pancreatic NETs responded with SD. None of the seven retinal angiomas demonstrated any shrinkage on ophthalmoscopy; however, two patients with retinal angiomas complained of increased hyperemia and eye discomfort during sunitinib treatment. When change in

Protocol 2011-0465 ASeptember 6, 2017 Page 10 of 50

lesion size was evaluated as a percentage by organ site per individual, RCC decreased a mean of 14.4% by the end of cycle four, NETs a mean 12.7%, and HB, 5.9% (Table 2). When size change was assessed as a continuous variable, both RCCs and NETs showed significant size decrease after four cycles of sunitinib therapy.

Forty-eight–week follow-up scans were obtained for renal lesions in five patients. In these patients, who had been finished with therapy for 6 months, RCC and NETs had regrown to close to baseline measurements but no larger (Table 2).

		Mean (Standard Error)						
	Baseline	Cycle 2	Percent	Cycle 4	Percent	Week 48	Percent	
Tumor Type	Size(cm)	Size (cm)	Change	Size (cm)	change	Size (cm)	change	
					-14.42		-3.37	
Renal Cell Carcinoma	2.41 (0.21)	2.04 (0.21)	-16.41 (3.9)	2.06 (0.22)	(4.5)	2.34 (0.24)	(5.7)	
P value		0.0004		0.0035		0.6098		
					-12.69		-1.72	
Pancreas NET	1.89 (0.28)	1.81 (0.28)	-3.59 (3.7)	1.64 (0.28)	(4.0)	1.89 (0.29)	(5.2)	
P value		0.284		0.011		0.959		
Hemangioblastoma	0.81 (0.08)	0.81 (0.08)	0.65 (3.4)	0.76 (0.08)	-5.9 (5.4)	0.76 (0.09)	-6.2 (5.4)	
P value		0.8	350	0.2	80	0.32	0	

Table 2. Mean Change from Baseline in Size of von Hippel-Lindau Lesions after Treatment with Sunitinib.	Table 2. Mean Change	e from Baseline	n Size of von	Hippel-Lindau	Lesions after	Treatment with Sunitinib.
---	----------------------	-----------------	---------------	---------------	---------------	---------------------------

#### 2.3.2 ARCHIVED TISSUE ANALYSIS

After obtaining IRB approval, we retrieved 20 sequential formalin-fixed and paraffinembedded specimens each of VHL-related HBs and sporadic RCCs at random from The University of Texas M. D. Anderson Cancer Center tissue bank. The specimens were analyzed at ApoCell, Inc. (Houston, TX), by using a laser-scanning cytometer (CompuCyte Corporation, Cambridge, MA), which is designed to enable fluorescencebased quantitative measurements on tissues at the single-cell level. This modality, like fluorescence-activated cell sorting analysis, provides multicolor immunofluorescenceintensity information from heterogeneous tissue specimens.

To detect biomarkers of interest, we incubated formalin-fixed tissues with CD31 (M0823, DakoCytomation), phosphorylated VEGFR2 (pVEGFR2; PC460, Calbiochem), VEGFR2 (SC-19530, Santa Cruz), FGFR3 (4574, Cell Signaling), Tie2 (334208, Biolegend),

Protocol 2011-0465 ASeptember 6, 2017 Page 11 of 50

pPDGFR-beta (SC-12909-R, Santa Cruz), PDGFR (SC-339-G, Santa Cruz), and pFRS2 (3864, Cell Signaling) antibodies, followed by species-specific secondary antibodies conjugated to fluorescent dyes (Cy5/FITC/PE; Jackson ImmunoResearch Laboratories). Each slide was placed on the computer-controlled motorized stage, and the area for scanning was visually located using the epifluorescence microscope of the cytometer, excluding normal and necrotic tissue regions. Slides were scanned using a 200× objective, and relative levels of fluorescence for each antigen were plotted on a scattergram. Results for biomarkers are represented as mean fluorescence intensity. Ratios of the fluorescence intensity of the phosphorylated to the total forms of VEGFR2 and PDGFR were also calculated. To detect signal in endothelial cells, relative fluorescence levels were assessed on a background of CD31 staining. For total tumor signal of antibody of interest, signal was assessed against a background of hematoxylin and eosin staining, in regions determined to be representative of tumor tissue.

The results of LSC on the archived tissue specimens from patients with VHL (20 untreated HBs and 20 untreated sporadic clear-cell RCCs) are summarized in Table 3. VEGFR2, pVEGFR2, and phosphorylated-to-total VEGFR2 ratios were statistically significantly higher in the RCC than in the HB samples. Conversely, FGFR3 and pFRS2 levels were higher in the HBs, with a strong trend in the endothelial cells (p=0.059) and significant differences in the overall tumor sample, with levels 11.45 (0.26) seen in HB vs. 11.26 (0.089) in RCC (P=0.003).

	log(H	[emangiobl	astoma)	log(l	RCC)		t-test	Wilcoxon' rank test
	N	mean	SD	N	mean	SD	p- value	p-value
pVEGFR2	20	11.268	0.498	20	11.752	0.378	0.001	0.003
VEGFR.total	20	12.977	0.478	20	13.081	0.859	0.639	0.192
pPDGFR	20	10.952	0.654	20	10.805	0.839	0.539	0.82
PDGFR.total	20	13.078	0.659	20	12.842	0.851	0.333	0.947
VEGFR.ratio	20	0.206	0.122	20	0.372	0.431	0.105	0.043
PDGFR.ratio	20	0.145	0.067	20	0.157	0.077	0.608	0.602

Table 3. Endothelial Receptor Levels in Hemangioblastomas and Renal Cell Carcinomas

								Wilcoxon'
	log(H	emangiobl	astoma)	log(I	RCC)		t-test	rank test
							p-	
	Ν	mean	SD	Ν	mean	SD	value	p-value
Tie2 in								
CD31PositiveCells	20	12.654	0.455	20	12.63	0.817	0.909	0.883
Tie2 in TumorCells	20	11.598	0.321	20	11.614	0.303	0.866	0.947
FGFR3 in								
CD31PositiveCells	20	12.265	0.448	20	12.29	0.961	0.914	0.495
FGFR3 in	20	11.439	0.224	20	11.338	0.106	0.075	0.174

Protocol 2011-0465 ASeptember 6, 2017 Page 12 of 50

TumorCells								
pFRS2 in CD31PositiveCells	20	12.495	0.492	20	11.91	0.989	0.023	0.059
pFRS2 in TumorCells	20	11.452	0.258	20	11.258	0.089	0.003	0.003

#### 2.4 Rationale for Current Study:

In our previous study we found that sunitinib, an oral small-molecule inhibitor of VEGFR, PDGFR, Flt3, and cKit, provides a consistent response in RCCs but not in CNS hemangioblastomas from patients with VHL. Endothelial VEGFR and FGFR are expressed differently in RCCs and HBs. Based on these observations, we would like to further expand our observations in VHL patients with measurable VHL lesions. We predict that pazopanib, an orally bioavailable small molecule inhibitor of VEGFR as well as other receptor tyrosine kinases, will provide at least the same benefit as sunitinib in a broad VHL patient population, but may provide superior overall quality of life. Phase III studies and MD Anderson Cancer Center clinical experience with pazopanib suggests that this agent may result in fewer toxicities when compared with sunitinib. As individuals with VHL need to balance the impact of disease progression on their overall outlook with the possible consequences of being on chronic therapy which produces continuous side effects, pazopanib may be an acceptable choice. In addition, although our initial clinical and tissue based observations suggest that sunitinib did not provide any clear shrinkage of hemangioblastomas in our clinical study, these observations require further validation. For this reason, we have chosen to proceed with a larger single arm study evaluating pazopanib in the treatment of patients with VHL, but will not exclude individuals with hemangioblastomas, nor will we make it a requirement for individuals who enroll on this study to have RCC.

Protocol 2011-0465 ASeptember 6, 2017 Page 13 of 50

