12.1 Design and sample size/power

In this study, we will treat up to 40 patients with VHL who have measurable VHL related lesions. Patients will receive Pazopanib 800mg PO daily for up to 24 weeks. Patients may choose to continue the regimen beyond 24 weeks until evidence of objective disease progression. Efficacy will be determined by the RECIST overall response rate (CR+PR) at 24 weeks. Early termination due to progressive disease or toxicity will be considered as a failure. Patients not completing 1 month of therapy due to a reason other than drug toxicity or progressive disease will be considered inevaluable. We will monitor for any lesion progression (PD) and drug discontinuation due to toxicity (DD) during the whole period of the treatment simutaneously. If there is a high probability that the PD rate exceeds 20% or the DD rate exceeds 10%, the trial will be stopped early and the drug will not be considered of interest for further study. Formally, the study will be terminated if Pr(PD Rate > 0.20 | Data) > 0.90 or Pr(DD)Rate > 0.10 | Data) > 0.90. The assumed prior distributions for PD rate and DD rate are Beta (0.2, 0.8) and Beta (0.1, 0.9), respectively, with one patient's worth of information. The study will be monitored in cohorts of 10 patients. Consideration to stop the trial will be given according to the stopping boundaries in Table 1. The operating characteristics for these stopping rules are summarized in Table 2, based on 10,000 simulations. Specifically, if the PD rate is 20% and DD rate is 0.10, then there is a 27% chance to stop the trial early and the average expected number of patients

Protocol 2011-0465 ASeptember 6, 2017 Page 48 of 50

treated will be 33. On the other hand, if (PD rate, DD rate) are (0.10, 0.05), or (0.10, 0.30), then the early stopping probabilities will be 3% and 94% and the average numbers of patients treated are expected at 39 and 16, respectively. If the trial continues to the end with 40 patients treated, we will be able to estimate the response rate at 24 weeks with standard error not larger than 0.08, i.e., the half length of the 95% confidence interval will not exceed 15%.

Total Number of Patients Treated	Stop if number of Progressions >=	Stop if number of Drug Discontinuation (due to Toxicity) >=
10	4	3
20	7	5
30	10	6

Table 1. Stopping boundaries for PD and DD monitoring.

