### 12.2 Analysis Plans

If the trial is stopped early, this drug will not be considered of interest for future study VHL patients. If all 40 patients are accrued, we will estimate the response rate, early progression rate, toxicity rate and their corresponding 95% posterior credible intervals.

Biomarker endpoints and genetic mutations will be measured at baseline and/or over time. Summary statistics, including frequency tabulation, means, standard deviations, median, and range, will be used to describe subject characteristics and marker data. The chi-squared ( $\gamma^2$ ) test or Fisher's exact test will be used to test the association between two categorical variables, such as response and prognostic factors and discrete markers. The association among various continuous and discrete markers and response may be assessed first by the exploratory data analysis graphically and tested using Wilcoxon rank sum test. Correlation among continuous biomarkers will be examined by Pearson or Spearman rank correlation coefficients. Both univariate and multivariate logistic regressions may be performed to model the baseline prognostic factors such as age, gender, race, smoking history, performance status, markers, etc, on response, when appropriate. We will also use the generalized estimating equations to model correlated discrete variables. Repeated measures analysis including mixed effects model will be performed to analyze continuous biomarkers change over time. Time to progression (TTP) will be estimated using the Kaplan-Meier method. Log-rank test will be performed to test the difference in survival between prognostic groups. Regression analyses of survival data based on the Cox proportional hazards model will be

Protocol 2011-0465 ASeptember 6, 2017 Page 49 of 50

conducted on TTP. The proportional hazards assumption will be evaluated graphically and analytically, and regression diagnostics (e.g., martingale and Shoenfeld residuals) will be examined to ensure that the models are appropriate.

Table 2. Operating characteristics for the stopping rules for excessive PD rate or DD rate

True PD Rate	True DD Rate	Probability of	Average Expected #
		Early	of Patients
		Termination	
0.10	0.05	0.03	39.2
0.30	0.05	0.57	25.8
0.20	0.10	0.27	33.1
0.30	0.10	0.61	24.6
0.30	0.15	0.71	22.1
0.10	0.20	0.64	25.7
0.20	0.20	0.70	23.4
0.30	0.20	0.84	18.9
0.10	0.30	0.94	16.3

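### Response is scored organ by organ, but Section 12 estimates only one pooled CR+PR rate, which moves with the tumour mix and leaves the hemangioblastoma question without an estimate.

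*Combined protocol and SAP*

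**What the plan says.** - **Rationale (2.4).** Pazopanib is predicted to be such that it "will provide at least the same benefit as sunitinib in a broad VHL patient population". The same section says that the lack of hemangioblastoma shrinkage on sunitinib needs validation, and cites this as a reason for a larger single-arm study. Hemangioblastoma patients are admitted and RCC is not required.
- **Prior data (2.3.1).** "Table 1 shows the best responses of individual lesions according to RECIST": partial response in 6 of 18 RCC lesions, 0 of 21 hemangioblastomas and 0 of 24 other lesions. Table 2 is a different summary, in which "lesion size was evaluated as a percentage by organ site per individual, RCC decreased a mean of 14.4% by the end of cycle four".
- **Measurement (11.1.5, 11.3.1).** Diameters are summed separately for kidney, pancreas, CNS and retina, because a single sum over all lesions would lose information. Target-lesion response is organ-specific.
- **Endpoint (12.1).** "Efficacy will be determined by the RECIST overall response rate (CR+PR) at 24 weeks".
- **Analysis (12.2).** With full accrual, "we will estimate the response rate, early progression rate, toxicity rate and their corresponding 95% posterior credible intervals". No response estimate by organ or lesion type is listed.
- **Second definition (11.3.3).** A note bases the response rate on CR+PR+SD, not CR+PR.

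**The concern.** The measurement section and the analysis section answer different questions. Section 11 keeps organs apart because they may respond differently. Section 12 then reports one number across patients whose measurable disease may be renal, CNS, pancreatic, retinal or adrenal. On the sunitinib data, those tumour types differ sharply in how often they shrink by 30%.

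Two consequences follow. First, the pooled rate reflects who enrols as well as what the drug does, and nothing in the plan fixes or adjusts for the mix. Second, the hemangioblastoma result that 2.4 wants to validate has no planned estimate. There is also a gap in definition. The overall-response table in 11.3.3 takes a single target-lesion entry, so it does not say what to record for a patient whose renal sum meets PR while the CNS sum is stable.

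**Working it through.** **1. The plan's own precision figure.** Section 12.1 states a standard error of at most 0.08 with 40 patients. sqrt(0.25/40) = 0.079, so this reproduces, and it confirms that the unit of the rate is the patient. The normal-approximation half-length is 1.96 × 0.079 = 15.5% at a rate of 50%, and is 15% or less for rates up to 37% or from 63%. The stated 15% is therefore close enough for what follows.

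**2. Inputs from the sunitinib Table 1 (counts).**
- RCC: 6/18 = 33.3%; exact 95% CI 13% to 59%.
- Hemangioblastoma: 0/21; exact upper limit 16%.
- Renal cyst 9, retinal angioma 7, pancreatic NET 5, pancreatic cyst 3: 0/24.
- All non-RCC lesions: 0/45; exact upper limit 8%. All lesions: 6/63 = 9.5%.

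These intervals treat lesions as independent. Clustering within patients would probably widen them.

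**3. Effect of mix on the pooled rate.** Assume that each patient is classed by one lesion type and that activity equals sunitinib's. Then pooled CR+PR = RCC share × 6/18 + (1 − RCC share) × 0. No enrolment mix is given, so the full range is shown.

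| RCC share | Expected CR+PR | Responders of 40 |
|---|---|---|
| 0% | 0% | 0 |
| 20% | 6.7% | 2.7 |
| 28.6% (18/63, the Table 1 lesion mix) | 9.5% | 3.8 |
| 50% | 16.7% | 6.7 |
| 80% | 26.7% | 10.7 |
| 100% | 33.3% | 13.3 |

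The range is 33 points with no difference in drug activity, against a stated half-length of 15 points.

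**4. Can mix reverse an informal ranking?** A drug half as active in RCC at an 80% RCC share gives 0.80 × 0.167 = 13.3%. An equally active drug at a 20% share gives 6.7%. The chance of at least 4 responders in 40 (10%, just above 9.5%) is 80% for the weaker drug and 28% for the equal one.

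**5. Effect of the missing organ-to-patient rule.** Take one RCC and one hemangioblastoma at the Table 2 mean baseline sizes, 2.41 cm and 0.81 cm. Suppose that the RCC shrinks by 30% and the hemangioblastoma does not change. The renal response is PR and the CNS response is SD. A sum over both organs changes by −0.30 × 2.41/(2.41 + 0.81) = −22.5%, which is SD. The same patient is a responder under an any-organ rule, and a non-responder under a summed or worst-organ rule.

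**6. Effect of the response definition.** Under CR+PR+SD, Table 1 gives RCC 16/18 = 89%, hemangioblastoma 19/21 = 90%, all other types 24/24 = 100%, and overall 59/63 = 94%. Mix then moves the rate by at most about 11 points, but the rate sits near its ceiling.

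**The case against.** The strongest reply is that no comparison with sunitinib exists to be distorted. The statement in 2.4 is background. Section 1.0 does not mention sunitinib, and Section 12 describes single-arm estimation with stopping rules for progression and toxicity, with no null rate, margin or historical reference. Section 2.5 itself doubts RECIST as a measure of success in VHL. This stands. A reader might infer that the pooled rate will be tested against sunitinib and that the mix decides the result; the documents support only an informal reading.

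A reader might also infer that the trial deliberately moves away from the sunitinib study's tumour mix. That is not supported. Table 1 already covers every eligible organ except adrenal, hemangioblastoma is its largest group, and that study's eligibility rules are not given beyond genetically proven VHL. The direction of any shift is unknown.

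It can also be said that organ-level work is already planned: 9.1 and 2.6 relate response to genotype by organ or lesion, and growth rate of target lesions is a secondary objective. The first two are exploratory genotype correlations, and the third concerns growth before and after treatment. None of them supplies a response rate by organ.

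Last, the size in the working depends on assumptions. Classing a patient by one lesion type simplifies a disease in which up to ten target lesions over several organs may be followed. The 9.5% is a lesion rate that the protocol does not state, and the mix effect shrinks under CR+PR+SD. All of this is fair. It limits the numbers to illustration, but it does not supply the missing estimates or the missing rule.

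**Conclusion.** The point holds as a gap between Sections 11 and 12. Organ-specific response is measured, but the only planned response estimate is one pooled CR+PR rate, without a rule for forming it from several organs. Assuming one lesion type per patient, sunitinib-like activity and the CR+PR definition, that rate could lie anywhere from 0% to 33% on RCC share alone. Under CR+PR+SD the range is about 11 points.

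The pooled rate is therefore hard to interpret, and it cannot inform the hemangioblastoma question or the prediction in 2.4. It does not follow that a planned inference is invalid, since no formal comparison with sunitinib is planned. Nor does it follow that the whole benchmark is lesion-level: Table 1 is, but Table 2 is by organ site per individual and lies closer to this trial's organ-specific sums.

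**What to change.** In 12.2:
- Add CR+PR at 24 weeks by organ, at least renal, CNS and pancreas, with 95% intervals. The denominator is patients with target lesions in that organ. State the interval method: some organs may have no responders, and 12.1 gives priors only for progression and toxicity discontinuation.
- Add mean percent change in the organ-specific sum of diameters at weeks 12 and 24. The mixed model in 12.2 is named for biomarkers, so extend it explicitly to lesion size.
- If lesion-level best response is also tabulated by type, allow for clustering within patients.
- Report retinal findings descriptively, since their assessment in 11.2 does not rest on diameters alone.

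In Sections 11 and 12, state how several organ responses become one patient response, and reconcile CR+PR (12.1) with CR+PR+SD (11.3.3). State also that only organ-specific results may be set beside the sunitinib tables, descriptively, noting that Table 1 is best response and not response at 24 weeks.

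The cost is analysis wording and a few tables; the CT and MRI measurements are already scheduled at the end of cycles 3 and 6. The drawback is wide intervals within each organ: 6 of 18, for example, has an exact interval of 13% to 59%.
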